## 2. GENERAL ANALYSIS DEFINITIONS

### 2.1. Visit Windows

Dosing days may be adjusted to accommodate the schedule of the site or the subject, as shown in [Table 1](#) below.

**Table 1: Study Drug (Dara-SC) Administration Schedule**

Cycle	Schedule	Day 1	Day 8	Day 15	Day 22
Cycle 1	Weekly	Day 1	Day 8 ( $\pm 1$ d)	Day 15 ( $\pm 1$ d)	Day 22 ( $\pm 1$ d)
Cycle 2	Weekly	Day 1 ( $\pm 3$ d)	Day 8 ( $\pm 1$ d)	Day 15 ( $\pm 1$ d)	Day 22 ( $\pm 1$ d)
Cycles 3-6	Every 2 weeks	Day 1 ( $\pm 3$ d)	—	Day 15 ( $\pm 1$ d)	—
Cycles 7+	Every 4 weeks	Day 1 ( $\pm 3$ d)	—	—	—

For analyses of data by cycle, if data are collected by date (e.g., AE onset), the corresponding study evaluations will be assigned to actual sequential cycles, which are derived from the study treatment administration data. The start date of a cycle is defined as the first scheduled dose date of the study treatment for that particular cycle, and the end date of a cycle is the start date of the next cycle minus 1. For the last cycle, the end date is defined as the end of treatment visit date. If the end of treatment visit date is not available, then the end date is either the last dose date plus 28 days or subsequent anticancer therapy start date minus 1 day, whichever comes first.

In general, if data (eg, laboratory etc) are collected by cycle, the nominal cycle will be used to summarize data. However, due to possible cycle delays, assessment performed in the same cycle may not be well aligned in time scale for different subjects. To address this, the following by-week windowing rules as specified in [Table 2](#) may be applied in the overtime data summary by study week.

**Table 2: Visit Window by Week**

Scheduled Study Visit	Time Interval (Week)	Time Interval (Study Day)	Target Time Point
Cycle 1 Day 1	Baseline	Day $\leq$ 1	1
Cycle 1 Day 8	Week 1	2 $\leq$ Day $\leq$ 9	8
Cycle 1 Day 15	Week 2	10 $\leq$ Day $\leq$ 16	15
Cycle 1 Day 22	Week 3	17 $\leq$ Day $\leq$ 23	22
Cycle 2 Day 1	Week 4	24 $\leq$ Day $\leq$ 30	29
Cycle 2 Day 8	Week 5	31 $\leq$ Day $\leq$ 37	36
Cycle 2 Day 15	Week 6	38 $\leq$ Day $\leq$ 44	43
Cycle 2 Day 22	Week 7	45 $\leq$ Day $\leq$ 51	50
Cycle 3 Day 1	Week 8	52 $\leq$ Day $\leq$ 58	57
Cycle 3 Day 15	Week 10	59 $\leq$ Day $\leq$ 72	71
Cycle 4 Day 1	Week 12	73 $\leq$ Day $\leq$ 88	85
Cycle 4 Day 15	Week 14	89 $\leq$ Day $\leq$ 100	99
Cycle 5 Day 1	Week 16	101 $\leq$ Day $\leq$ 116	113

Cycle 5 Day 15	Week 18	$117 \leq \text{Day} \leq 128$	127
Cycle 6 Day 1	Week 20	$129 \leq \text{Day} \leq 144$	141
Cycle 6 Day 15	Week 22	$145 \leq \text{Day} \leq 156$	155
Cycle 7 Day 1	Week 24	$157 \leq \text{Day} \leq 172$	169
Cycle 8 Day 1	Week 28	$173 \leq \text{Day} \leq 200$	197
Cycle 9 Day 1	Week 32	$201 \leq \text{Day} \leq 228$	225
Cycle 10 Day 1	Week 36	$229 \leq \text{Day} \leq 256$	253
... ...	...	...	...
Cycle X Day 1	Week $4*(X-1)$	$(X-1)*28 - 23 \leq \text{Day} \leq (X-1)*28 + 4$	$(X-1)*28 + 1$

## 2.2. Pooling Algorithm for Analysis Centers

All participating centers in the study will be pooled together for analyses.

## 2.3. Analysis Sets

### 2.3.1. Efficacy Analysis Set(s)

#### 2.3.1.1. Primary Efficacy Analysis Set

Intent-to-treat (ITT) analysis set: defined as all subjects randomized into the study. This analysis set will be used for summary of study populations, analyses of disposition, demographic, baseline disease characteristics, and analyses of efficacy endpoints. All subjects in ITT analysis set will be analyzed according to their randomized treatment group, regardless of the actual treatment received.

#### 2.3.2. Safety Analysis Set

Safety analysis set: defined as all randomized subjects for subjects randomized to active monitoring or all randomized subjects who received at least one dose of daratumumab for subjects randomized to daratumumab. This analysis set will be used for all safety analyses and analyses of exposure. All subjects in safety analysis set will be analyzed according to the actual treatment that they received.

#### 2.3.3. Pharmacokinetics Analysis Set

Pharmacokinetics analysis set: defined as subjects who received at least 1 administration of daratumumab and have at least 1 pharmacokinetics sample concentration value after the first injection. All pharmacokinetic parameters will be analyzed based on the pharmacokinetics analysis set.

### 2.3.4. Immunogenicity Analysis Set

Immunogenicity-evaluable analysis set:

- Daratumumab immunogenicity-evaluable: Immunogenicity-evaluable analysis set for antibodies to daratumumab is defined as all subjects who receive at least one dose of Dara-SC and have appropriate serum samples for detection of anti- daratumumab antibodies.
- rHuPH20 immunogenicity-evaluable: Immunogenicity-evaluable analysis set for antibodies to rHuPH20 is defined as all subjects who receive at least one dose of Dara-SC and have appropriate plasma samples for detection of anti- rHuPH20 antibodies.

### 2.4. Definition of Subgroups

In general, subgroup analyses on the pre-specified subgroups in [Table 3](#) will be performed for the primary efficacy endpoint PFS, and selected treatment-emergent adverse event (TEAE).

**Table 3: Subgroup Analyses for Efficacy and Safety Endpoints**

Subgroup	Definition	Analysis Type
Sex	Male, Female	E, S
Age	E: <65, ≥65 years S: < 65, 65 to < 75, and ≥ 75 years	E, S
Race	White, non-white	E, S
Region	Western EU + US, other	E, S
Weight	≤ 65 kg, > 65 to 85 kg, and >85 kg	E, S
Baseline renal function (GFR (mL/min/1.73m  )) a	S: Normal vs Abnormal	E, S
Baseline hepatic function	Normal, Impaired b	S
Risk factors associated with progression to MM c	< 3 vs ≥3	E
ISS staging d	I, II, III	E
Cytogenetic risk at study entry(Yes/No)	Yes, if del(17p13), amp(1q21), t(4;14), or t(14;16) abnormality detected at baseline, No, if subjects tested for these probes but did not have any of the abnormalities	E
Mayo 2018 risk criteria e	Low, intermediate, or high	E
ECOG score	0 vs 1	E

E: efficacy (PFS); S: safety (TEAE)

a Normal: GFR (mL/min/1.73m^2) ≥ 90

b Hepatic impairment status is classified into 4 levels per NCI Organ Dysfunction: normal (total bilirubin ≤ ULN and AST ≤ ULN); mild (total bilirubin ≤ ULN and AST > ULN) or (ULN < total bilirubin ≤ 1.5×ULN); moderate (1.5×ULN < total bilirubin ≤ 3×ULN); and severe (total bilirubin > 3×ULN). Impaired includes mild, moderate and severe.

c Risk factors: a. Serum M protein ≥30 g/L, b. IgA SMM, c. Immunoparesis with reduction of 2 uninvolved immunoglobulin isotypes (only IgA, IgM, and IgG should be considered in determination for immunoparesis; IgD

and IgE are not considered in this assessment), d. Serum involved: uninvolved FLC ratio  $\geq 8$  and  $< 100$ , e. Clonal BMPCs  $> 50\%$  to  $< 60\%$  with measurable disease.

dISS: Stage I: Serum beta-2 microglobulin  $< 3.5$  mg/L and serum albumin  $\geq 3.5$  g/dL; Stage II: Not stage I or stage III; Stage III: Serum beta-2 microglobulin  $\geq 5.5$  mg/L

e Mayo 2018 risk criteria:

- Serum M protein  $> 2$  g/dL
- I/U FLC ratio  $> 20$
- BMPC  $> 20\%$

Patients with presence of

- 0 factors are considered as low risk
- 1 factor are considered as intermediate risk
- $\geq 2$  factors are considered as high risk

## 2.5. Study Day and Relative Day

Study day or relative day is defined as: date of assessment – first dosing date + 1 for any assessment done on or after first dosing date for subjects on the daratumumab arm and date of assessment – randomization date + 1 for any assessment done on or after randomization for the active monitoring arm; otherwise, study day is defined as date of assessment – first dosing date/randomization date, depending on whether subject was in the daratumumab arm or the active monitoring arm. The first dose date is defined as the earliest date of non-zero dose of study drug.

## 2.6. Baseline

The baseline value is defined as the last non-missing measurement taken on or prior to the first dose administration of daratumumab (including time if time is available) for the treatment arm or randomization for the active monitoring arm.

## 2.7. Imputation of Missing Data

### 2.7.1. Adverse Event Start and End Date

#### Adverse Event Start Date

If the onset date of an adverse event is completely or partially missing, the following imputation rules will be used.

- When month and year are present, and the day is missing:
  - If the onset month and year are the same as the month and year of first dosing date, the day of first dosing or the day-component of the AE end date (possibly imputed) is imputed, whichever is earlier;
  - If the onset month and year are not the same as the month and year of first treatment with study drug, the first day of the month is imputed.
- When only a year of the onset date is present:
  - If the onset year is the same as the year of first treatment with study drug:

- If AE end date is available and is prior to first dosing date, the day and month of AE end date are imputed;
- Otherwise, the day and month of the first dosing date are imputed.

- If the onset year is different from the year of first treatment with study drug, the 1st of January is imputed.

- If the onset date is completely missing, the first dosing date is imputed as the onset date.

No imputation will be done for partial or missing AE onset time.

#### Adverse Event End Date

If the end date of an adverse event is completely or partially missing, the following imputation rules will be used.

- If month and year are present and the day of the month is missing, the last day of the month is imputed.
- If only a year is present, the 31st of December is used.
- If date is completely missing, no imputation will be done.

After the imputation, if the imputed date is later than the date of death (if available), the date of death will be used as the imputed date.

No imputation will be done for partial or missing AE end time.

#### **2.7.2. Prior and Concomitant Medication/Therapy Start and End Date**

For prior or concomitant medications/therapy, if the start or end date is completely missing, no imputation will be performed. If the start or end date is partially missing, the following imputation rules will be used.

- If only the day is missing, the 15th day of the month will be used.
- If both the day and month are missing, the 30th of June will be used.

If the medication/therapy was taken prior to study start, and the imputed start date is after first dosing date, further adjust the imputed start date as the day prior to first dosing date; if the medication/therapy was taken after study start, and the imputed start date is prior to first dosing date, further adjust the imputed start date as first dosing date. Also adjust the imputed medication/therapy end date so that it is on or after first dosing date.

### **2.7.3. Smoldering Multiple Myeloma/First M-protein Detection Diagnosis Date**

If the diagnosis date of smoldering multiple myeloma (SMM) or first M-protein detection date is completely missing, no imputation will be applied. If the diagnosis date or first M-protein detection date is partially missing, the following imputation rules will be applied:

- If only the day of the diagnosis date or first M-protein detection date is missing, impute day of diagnosis date or first M-protein detection date with 15;
- If both month and day of the diagnosis date or first M-protein detection date are missing, impute the month and day of the diagnosis date or first M-protein detection date with June 30.

### **2.7.4. Partial Subsequent Anticancer Therapy Start Date**

If year or month of subsequent anticancer therapy start date is missing or no components of the start date are present, no imputation will be performed.

If only the day-component is missing, the following steps apply:

- If the month and year of the start date are the same as the month and year of last dosing date, the day of last dosing date or the day-component of the stop date of subsequent anticancer therapy is imputed, whichever is earlier.
- If the start month and year are not the same as the month and year of last dosing date, the first day of the month is imputed.

After applying above adjusting method, if it results that the start date is after the subsequent anticancer therapy end date, the start date needs to be re-adjusted to be the same as the end date. No imputation will be applied for missing or partial subsequent anticancer therapy end date.

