9.1.4. Follow-Up Phase

The Follow-up Phase will begin once the subject completes 39 cycles or 36 months (whichever occurs first) of active monitoring (Arm A) or daratumumab treatment (Arm B). Reasons for premature discontinuation of active monitoring or daratumumab treatment are listed in Section 10.2. Subjects who discontinue before PD must continue to have disease evaluations as described in Section 9.2, until study completion or confirmed PD (or other reasons as outlined in Section 10). If subjects have not progressed to MM, then no other treatment for SMM or MM is allowed during the study. Follow-up for first-line MM treatment (including the response to first-line MM treatment), second primary malignancies, and survival status will be obtained as specified in the Time and Events Schedule (Table 1). Survival will be followed until the end of the study and at a frequency of at least every 12 weeks until PD. After PD, survival is to be followed at least every 6 months, until the end of the study.

If PRO or survival information is obtained via telephone contact, then written documentation of the communication must be available for review in the source documents. If the subject has died, then the date and cause of death will be collected and documented in the eCRF.

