## 5.2. Primary Efficacy Endpoint(s)

### 5.2.1. Definition

The primary endpoint of this study is PFS as assessed by the independent review committee (IRC), defined as the duration from the date of randomization to either progression to multiple myeloma, according to the IMWG diagnostic criteria for MM, or death due to any cause, whichever occurs first. Progression evaluations for the primary endpoint/final analysis were based on IRC review, in a blinded fashion, to objectively and consistently implement the IMWG diagnostic criteria for MM. Data from the central laboratory, local clonal plasma cell assessment and images performed at the study site (or designated facility) assessed by independent radiological review were provided to IRC for progressive disease identification. Subjects who start anti-cancer therapies for multiple myeloma without disease progression will be censored at the last disease assessment before the start of subsequent therapies. Subjects who withdraw consent from the study before disease progression will be censored at the last disease assessment before withdrawal of consent to study. Subjects who are lost to follow-up will be censored at the last disease assessment before the subjects were lost to follow-up. Subjects who have not progressed and are still alive at the clinical cut-off date for analysis will be censored at the last disease assessment. Subjects without any post-baseline disease assessment will be censored at randomization.

Determination of dates of PFS event and dates for censoring is summarized in [Table 4](#) as follows.

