**Table 4: PFS Event and Censoring Method**

Situation	Date of Progression or Censoring	Outcome
No postbaseline disease assessment	Randomization	Censored
Disease progression prior to start of anti-cancer therapy for multiple myeloma	Earliest date that indicates disease progression	PFS event
Death prior to start of anti-cancer therapy for multiple myeloma	Date of death	PFS event
Other, such as: 
 
○ Withdrawal of consent to study participation,
 
○ Lost to follow-up
 
○ Start of subsequent anti-cancer therapy prior to disease progression or death
 
	Date of last disease assessment on or prior to withdrawal of consent to study participation, lost to follow-up, or start of subsequent anti-cancer therapy	Censored

Note, Subjects who were already diagnosed multiple myeloma per baseline central imaging review will be censored at randomization.

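### A subsequent-therapy start date with a missing day is imputed with no check against the progression date, so a PFS event can become a censoring when therapy starts in the month of progression

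*SAP*

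**What the plan says.** SAP 2.7.4 covers a subsequent-therapy start with month and year known and the day missing. It has two branches:

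- Start month same as last-dose month: "the day of last dosing date or the day-component of the stop date of subsequent anticancer therapy is imputed, whichever is earlier".
- Any other month: the first of that month, as in "month and year of last dosing date, the first day of the month is imputed".

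One later adjustment applies. If the imputed start falls after the end of that therapy, "the start date needs to be re-adjusted to be the same as the end date". This can only move the start earlier. The section never mentions the progression date, and it gives no reference date for subjects on active monitoring, who receive no study drug (Protocol section 6).

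The date then enters the primary endpoint. In SAP Table 4 the event row reads "Disease progression prior to start of anti-cancer therapy for multiple myeloma", and the censoring row includes "Start of subsequent anti-cancer therapy prior to disease progression or death". Under SAP 5.2.1, subjects who start therapy without progression "will be censored at the last disease assessment before the start of subsequent therapies". Disease evaluations are 12 weeks apart (SAP 1.2).

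**The concern.** Protocol 9.1.4 sets the expected order of events: "If subjects have not progressed to MM, then no other treatment for SMM or MM is allowed during the study". When therapy and progression fall in the same month and the day of therapy is unrecorded, the likely order is progression first. The imputation can assign the opposite order. The progression then fails the Table 4 event condition, and the subject is censored at an earlier assessment. Because progression itself prompted the therapy, this censoring is informative.

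Other parts of the SAP handle comparable problems. Section 2.7.5 ties partial PFS2 dates to the start dates of first- and second-line therapy. Section 2.7.2 corrects imputed medication dates that contradict known timing. Sections 2.5 and 2.6 substitute randomization for the first dose in Arm A. Section 2.7.4 has no equivalent of any of these.

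The same date is used elsewhere. It sets censoring for BOD-PFS (5.3.1.1) and duration of response (5.3.8.1). It is itself the event date for time to first-line treatment (5.3.4.1). It also affects PFS2, which censors subjects who begin first-line therapy without progression on study (5.3.5.1). PFS2 is in the alpha-controlled hierarchy (5.1.1), and its final analysis comes after the primary analysis.

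**Working it through.** **1. The plan's own figure.** Inputs from SAP 1.4 and 1.5: HR 0.625, two-sided alpha 0.05, power 85%, 1:1 allocation. Schoenfeld: 4(1.960 + 1.036)² / (ln 0.625)² = 163 events. Freedman gives 169. At 165 events the Schoenfeld power is 85.5%. The planned 165 is reproduced.

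**2. The rule applied to one case.** Progression on 10 March, true therapy start on 20 March, day missing:

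| Last dose | Imputed start | Result under Table 4 |
|---|---|---|
| None (Arm A, if the first-of-month branch is applied) | 1 March | Censored before 1 March |
| 14 February (Arm B) | 1 March | Censored before 1 March |
| 3 March (Arm B) | 3 March | Censored before 3 March |
| 10 March (Arm B) | 10 March | Tie; neither row applies |

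Both branches can misorder, so Arm B is exposed as well.

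**3. How often a day-missing record is misordered.** The first-of-month rule was applied to every possible progression date in a four-year calendar, with fixed gaps from progression to therapy:

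| True gap (days) | Misordered |
|---|---|
| 0 | 97% |
| 7 | 74% |
| 14 | 51% |
| 21 | 28% |
| 28 | 5% |
| 30 or more | 0% |

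Progression on the first of the month gives a tie (about 3% of dates at gaps up to 28 days).

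**4. Expected number affected.** The documents give neither the missing-day rate nor the gap, so these are assumptions: 150 progressions, all followed by therapy, and an exponential gap with mean m days. P(same month) = 1 − (m/30.44)(1 − exp(−30.44/m)), which is 0.37 for m = 30 and 0.22 for m = 60. Ties are included.

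- Low: 150 × 0.02 × 0.22 = 0.66, about 0.7 events.
- High: 150 × 0.05 × 0.37 = 2.78, about 2.8 events.
- Adverse corner: m = 14 gives 0.59, and 150 × 0.05 × 0.59 = 4.4 events.

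The result depends on the shape of the gap distribution. If every gap were 30 days or more, no record would be misordered.

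**5. Effect on the comparison.** If shares f of Arm A events and q of Arm B events are lost, HR is approximately 0.625 × (1 − q)/(1 − f).

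| Arm A loss only (q = 0) | HR | Power at 165 events |
|---|---|---|
| 1% | 0.631 | 84.0% |
| 2% | 0.638 | 82.4% |
| 5% | 0.658 | 76.7% |
| 10% | 0.694 | 64.9% |

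For scale, the design medians with 24 months of accrual and 24 of follow-up give 100.6 expected events in Arm A and 72.4 in Arm B. At 165 events Arm A therefore has about 165 × 100.6/173.1 = 95.9. If all 2.8 events were lost from Arm A, f = 2.8/95.9 = 2.9%, between the 2% and 5% rows. Equal loss in both arms keeps the HR near 0.625. At a fixed cutoff, power is then 85.2%, 83.7% or 81.7% for 1%, 5% or 10% lost.

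**The case against.** The strongest case on the other side has five parts.

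**Not every reordered case is wrong.** A reader might infer that, because the protocol forbids therapy before progression, each one is a misclassification. The documents do not support that. Protocol 9.1.4 is a conduct rule, and treatment decisions follow the investigator's finding of progression (Protocol 9.1.3 and 10.2), whereas the primary endpoint uses blinded IRC progression. Therapy can truly precede the IRC date. SAP 5.2.2 lists therapy before progression as an intercurrent event, and in those cases censoring is what the plan intends. This stands, and it limits both the claim and the remedy.

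**The problem is not confined to Arm A.** A reader might also infer that the last-dose branch protects Arm B. It does not, as two Arm B rows of the example show, and Arm B subjects whose last dose was in an earlier month fall under the first-of-month rule. Arm A may lose more events because more progressions are expected there, but that would move the HR toward 1 and so would not favour daratumumab.

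**A mitigation is planned.** Supplemental analysis 2 in SAP 5.2.3 does not censor at subsequent therapy, so it recovers these events. It also stops censoring genuine pre-progression therapy, so it cannot isolate the imputation error, and the primary result is unchanged.

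**The count may be zero.** Missing days can be queried (Protocol 17.5 and 17.6). Confirmation of progression and medical-monitor review (Protocol 9.2 and 10.2) may lengthen the gap. Because the analysis is event-driven, lost events mainly delay the cutoff. This stands as to size.

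**Changing the rule now is post hoc for PFS.** Protocol Amendment 6 says the primary analysis has concluded and the study was unblinded. This also stands, and the fix is framed accordingly.

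**Conclusion.** The point holds as a gap in a stated rule. SAP 2.7.4 read with Table 4 can date therapy before a progression in the same month and convert a PFS event into a censoring, in either arm. It also leaves the Arm A reference date undefined and same-day ties unresolved.

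The size is unknown and probably small: about 0.7-2.8 events of 165 on the stated assumptions, and possibly none. The 4.4 figure needs a short gap combined with 5% missing days. The documents do not show that the primary conclusion was affected. Any imbalance toward Arm A would dilute the estimated effect. Exposure of the response cut-off for ORR is marginal, because a first response would have to fall in the same month as the start of therapy. This is worth correcting, but it does not undermine the design.

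**What to change.** Amend SAP 2.7.4 for starts with only the day missing:

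- If investigator-documented progression (the progression that triggers therapy) falls in the same month, impute no earlier than the day after it. If it falls on the last day of the month, use that day.
- Otherwise, impute the first of the month, but no earlier than the last dose date (Arm B) or randomization (Arm A) where that date falls in the month.
- Cap the result at the therapy end date.
- Use this one imputed date for the IRC, investigator and algorithm versions of PFS and for the other endpoints that depend on it.
- State in Table 4 that progression on the same date as therapy start counts as an event.
- Leave fully recorded therapy starts before progression censored as now.

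Since the primary analysis has concluded, list every subject whose imputed start falls in the month of progression, by arm, and report PFS with them reclassified as a sensitivity analysis labelled post hoc. An empty listing closes the point for PFS. Put the corrected rule in place before the final PFS2 analysis.

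The cost is a short SAP amendment, one listing and one rerun. No new data are needed.
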